4.2 Exclusion Criteria

Patients who meet any of the following criteria will be excluded from participation in the study:

1. Homozygous familial hypercholesterolemia;
2. Low-density lipoprotein (LDL) or plasma apheresis within 2 months prior to randomization;
3. New York Heart Association class III or IV heart failure, or known left ventricular ejection fraction $<30\%$;
4. Uncontrolled cardiac arrhythmia, including confirmed QT interval corrected using Fridericia's formula (QTcF) >450 msec for males and >470 msec for females at the screening electrocardiogram (ECG) assessment;

5. Myocardial infarction, unstable angina, percutaneous coronary intervention, coronary artery bypass graft, or stroke within 3 months prior to randomization;
6. Type 1 diabetes, or newly diagnosed or uncontrolled type 2 diabetes (hemoglobin A1c [HbA1c] >8%);

7. History of significant alcohol consumption for a period of more than 3 consecutive months within 1 year prior to screening;

Note: Significant alcohol consumption is defined as average of >20 g/day in female patients and >30 g/day in male patients;

8. Hyperthyroidism;
9. Thyroid replacement therapy
10. Hypothyroidism;

Note: If TSH is up to 1.5 x ULN on screening with normal free T4, one repeat test is allowed to confirm the elevation in TSH. If TSH and free T4 are normal upon repeat testing, patient may be included. Patients with a history of thyroid hormone replacement therapy or patients who have discontinued thyroid hormone replacement therapy (including thyroxine) ≥ 2 months prior to randomization may be included in the study if this criterion is met;

11. Evidence of chronic liver disease;
12. Hepatitis B, as defined by the presence of hepatitis B surface antigen (HBsAg);
13. Hepatitis C, as defined by the presence of hepatitis C virus (HCV) antibody (anti-HCV) and HCV ribonucleic acid (RNA). Patients with positive anti-HCV who test negative for HCV RNA at screening will be allowed to participate in the study;
14. Serum ALT $>1.5 \times$ ULN (one repeat allowed);
15. Estimated glomerular filtration rate <60 mL/min;
16. Creatine kinase $>3 \times$ ULN (one repeat allowed);
17. History of biliary diversion;
18. Positive for human immunodeficiency virus (HIV) infection;
19. History of malignant hypertension;
20. Systolic blood pressure >160 mmHg or diastolic blood pressure >100 mmHg at screening or randomization and confirmed at an unscheduled visit;

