9.13 Drug Induced Liver Injury Monitoring

With any of the following liver function test elevations, patients should undergo repeat laboratory measurements as soon as possible, preferably within 72 hours (unless otherwise specified), and no later than 1 week. Local laboratory measurements may be used to facilitate follow-up:

- ALT or AST $>8 \times$ ULN;
- ALT or AST $>3 \times$ ULN and bilirubin $>2 \times$ ULN or International Normalized Ratio $>1.5 \times$ ULN;
- ALT or AST $>3 \times$ ULN with the appearance of fatigue, nausea, vomiting, right upper quadrant pain or tenderness, fever rash, and/or eosinophilia ($>5\%$); and
- ALT or AST $>5 \times$ ULN, regardless of symptoms should be followed up within 1 week.

Repeat evaluation should include AST, ALT, prothrombin time/International Normalized Ratio, total bilirubin, alkaline phosphatase, gamma-glutamyltransferase, creatinine, CK, and complete viral hepatitis screen. The patient should be questioned regarding symptoms, as well as potential causative factors. This information, including results and normal ranges of any laboratory parameters collected at a local laboratory, should be collected on the appropriate eCRF. Hepatobiliary ultrasonography and/or consultation with a hepatologist should be considered if clinically indicated.

Abnormal laboratory parameters should be followed at least weekly (more frequently as clinically indicated) until they have returned to baseline or have stabilized.

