3.8.2 Clinical Laboratory Assessments

3.8.2.1 Chemistry and Hematology

Descriptive statistics of each chemistry and hematology parameter will be presented for baseline values and for values and changes from baseline at each post-baseline visit. These will be presented by treatment group for each parameter using the Safety Population.

Counts and percentages of patients with any post-baseline observation that is below the lower limit of normal (<LLN) or above the upper limit of normal (>ULN) will be summarized for each chemistry and hematology parameter by treatment group and overall.

The liver enzyme parameters (ALT, AST, creatine kinase [CK], and GGT) will be analyzed for the overall Safety Population by active and placebo groups, and by exposure group, final dose group, and SHBG group. Statin subgroup will also be explored. Patients with mild liver diseases will not be included in the analysis of liver enzyme parameters, since the liver enzyme value will be affected. The possible liver disease may include, but is not limited to: elevated

liver enzymes (elevated direct bilirubin ≥ 0.3 mg/dL, or GGT > 100 U/L) or large amount of alcohol use.

The shift from baseline value to the worst post-baseline value will be summarized for selected parameters (AST, ALT, total bilirubin, alkaline phosphatase, creatinine, and CK). Shift categories will be based on normal ranges (<LLN, Normal, >ULN).

3.8.3 12-Lead Electrocardiogram

ECG parameters (heart rate, PR interval, QRS interval, QT interval, QTcB interval, QTcF interval, RR Interval, and overall interpretation) will be summarized by treatment group using descriptive statistics for the Safety Population. The average of 3 readings will be used in the summaries. For the overall interpretation, the most severe interpretation at the visit will be summarized. The count and percentage of patients with QTcF and/or QTcB above thresholds (>450 msec, >480 msec, >500 msec) or change from baseline above thresholds (>30 msec, >60 msec) will be summarized by treatment group for the Safety Population.

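### The SAP's liver tables have one open-ended class above normal, so they give no patient counts by arm at the protocol's own ALT/AST and bilirubin thresholds

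*SAP*

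**What the plan says.** SAP 3.8.2.1 plans these laboratory outputs for the Safety Population:

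- Descriptive statistics of "values and changes from baseline at each post-baseline visit". SAP 3.1 defines these to include the maximum.
- A table of how many patients in each group, and what share, had "any post-baseline observation that is below the lower limit of normal (<LLN) or above the upper limit of normal (>ULN").
- A separate analysis of ALT, AST, CK and GGT by active and placebo group, exposure, final dose and SHBG group. It leaves out patients with mild liver disease, for example GGT above 100 U/L or direct bilirubin of 0.3 mg/dL or more.
- A shift table: "The shift from baseline value to the worst post-baseline value will be summarized for selected parameters". The six chosen are CK, creatinine, ALT, AST, alkaline phosphatase and total bilirubin, and one sentence fixes the classes for all of them: "Shift categories will be based on normal ranges (<LLN, Normal, >ULN").

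The protocol works in multiples of ULN. Exclusion 14 (Section 4.2) reads "Serum ALT $>1.5 \times$ ULN (one repeat allowed"), so ALT above ULN and up to 1.5×ULN is eligible. No AST limit is listed. Section 9.13 sets repeat-testing rules at "ALT or AST $>8 \times$ ULN", at "ALT or AST $>3 \times$ ULN and bilirubin $>2 \times$ ULN" (or INR >1.5×ULN), at >3×ULN with listed symptoms or eosinophilia, and finally "ALT or AST $>5 \times$ ULN, regardless of symptoms should be followed up within 1 week".

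Protocol 10.2.2 also promises a summary of laboratory abnormalities considered of special interest. Neither document defines these, and the SAP does not carry the item forward.

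**The concern.** The protocol treats liver enzymes as a central class concern. Section 1.1 lists enzyme elevations among the reasons why earlier thyroid agonists were stopped, Section 1.1.2 is given over to the subject, and Section 9.13 sets graded rules for follow-up. The planned categorical tables do not use that grading. With one class above ULN, a patient who starts above ULN cannot move up. A patient who starts normal moves to the same cell whether the rise is trivial or large.

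What is at stake is how readable the liver result is. The clinical study report could state how many patients in each arm went above ULN. It could not state, from the tables the SAP describes, how many passed 3×, 5× or 8×ULN, or how many had raised ALT/AST together with raised bilirubin.

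**Working it through.** The SAP states no figure here to reproduce. The check is a classification exercise, followed by a rough scale from the protocol's own data.

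**1. Classification.** Inputs are the SAP classes and cuts at 3×, 5× and 8×ULN from Protocol 9.13. The example values are illustrative.

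| Baseline → worst (×ULN) | SAP classes | Cuts at 1, 3, 5, 8×ULN |
|---|---|---|
| 1.4 → 1.45 | >ULN → >ULN | >1–3 → >1–3 |
| 1.4 → 3.1 | >ULN → >ULN | >1–3 → >3–5 |
| 1.4 → 5.1 | >ULN → >ULN | >1–3 → >5–8 |
| 1.4 → 8.0 | >ULN → >ULN | >1–3 → >5–8 |
| 1.4 → 8.1 | >ULN → >ULN | >1–3 → >8 |
| 0.8 → 1.1 | Normal → >ULN | Normal → >1–3 |
| 0.8 → 8.1 | Normal → >ULN | Normal → >8 |

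The first five rows fall in one SAP cell although the fold rise runs from 1.45/1.4 = 1.04 to 8.1/1.4 = 5.8. The last two rows also share a cell. The 8× rule is strict, so exactly 8.0× meets the >5× rule and not the >8× rule.

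**2. How many patients could start above ULN.** Protocol Table 1 gives baseline ALT in the ULN–2×ULN band for the Phase 3 eprotirome trial in HeFH: 3 of 23 (placebo), 6 of 24 (50 µg) and 2 of 22 (100 µg).

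- Pooled: (3 + 6 + 2)/(23 + 24 + 22) = 11/69 = 15.9%.
- Applied to 105 patients: 0.159 × 105 = 16.7, about 17. Applied to the 70 on MGL-3196: 0.159 × 70 = 11.2, about 11.
- Range across the three arms' rates: 2/22 × 105 = 9.5 to 6/24 × 105 = 26.3.

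The band runs to 2×ULN and entry here stops at 1.5×ULN, so the pooled figure is an upper estimate. It counts patients who could show no upward shift, not patients expected to have a large rise.

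**3. What one class loses.** In the same table, week-6 ALT on eprotirome 100 µg was normal in 4, 1–2× in 11, 2–3× in 3, 3–4× in 3 and 4–5× in 1. The sum is 22, which matches the arm size. The SAP's count table would show 11 + 3 + 3 + 1 = 18 above ULN. The 3 + 1 = 4 patients above 3×ULN would not be separable from the other 14.

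**4. Practice elsewhere in the SAP.** SAP 3.8.3 counts patients with QTc above 450, 480 and 500 msec. Graded thresholds are already used for that safety measure but not for the liver.

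**The case against.** The strongest reply is that a large rise would not be lost. It would appear in the by-visit maximum value and maximum change, in the patient listings (SAP Section 5), in the adverse event tables if the investigator judged it clinically significant (Protocol 9.1), in the 9.13 work-up on the eCRF, and before the DSMB. With about 105 patients, a reader could pick out the few extreme cases. This stands, and it limits the point. But a maximum is one value per visit and arm: it gives no number of patients and does not link ALT/AST to bilirubin in the same patient. Adverse event reporting depends on judgment.

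Protocol 9.13 also governs repeat testing, not analysis classes, so the SAP does not contradict it. That is correct; the finding is a gap in tabulation, not a conflict. The table shells are stand-alone documents not available here, and the special-interest item in Protocol 10.2.2 might be meant to cover the gap. But the item is undefined and absent from the SAP, and the SAP text that should govern the shells names three classes.

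A reader might infer three stronger things, none of which the documents support:

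- *That the planned tables cannot repeat the protocol's comparison with eprotirome.* Table 1 shows MGL-3196 only as normal or >ULN, and the stated comparison is at >1×ULN, which the SAP's counts can repeat.
- *That patients with raised baseline ALT are invisible.* They appear in the >ULN baseline row; only the size of a further rise is lost.
- *That a serious liver signal cannot be seen, or that the safety objective goes unanswered.* The other outputs listed above rule this out.

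**Conclusion.** The point holds as a cheap and worthwhile improvement. As written, SAP 3.8.2.1 gives no patient count by arm at any of the Protocol 9.13 liver thresholds, and its shift table cannot register a rise in a patient who starts above ULN.

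About 17 of 105 patients could be affected for ALT. This assumes that baseline ALT resembles the eprotirome HeFH trial and that the 1.5×ULN limit holds at Day 1. The limit allows one repeat, and the SAP baseline is the Day 1 value, so some baselines could differ from the value that qualified the patient. How many large rises would actually be masked cannot be derived from the documents.

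**What to change.** In SAP 3.8.2.1, by arm and in the full Safety Population:

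1. Count patients meeting each Protocol 9.13 criterion at any post-baseline time: ALT or AST >3×ULN with bilirubin >2×ULN; >3×ULN with INR >1.5×ULN; >3×ULN with the listed symptoms or eosinophilia; >5×ULN; and >8×ULN. State how close in time the components must be, and whether unscheduled and local-laboratory repeats count.
2. Split the >ULN shift class, for example into >1–3×, >3–5×, >5–8× and >8×ULN for ALT and AST, and >1–2× and >2×ULN for bilirubin. A rise within 1–3×ULN would still show no shift; a further cut at the 1.5× entry limit would expose part of it.
3. State that the mild-liver-disease exclusion does not apply to these tables. It is not limited to baseline findings, so an on-treatment rise in GGT or direct bilirubin could otherwise remove the patient concerned.
4. Define the special-interest laboratory abnormalities of Protocol 10.2.2, or state that item 1 serves as that summary.

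ALT, AST and bilirubin are in the chemistry panel at every visit, so no new data are needed for those. INR is scheduled after baseline only at Week 12 or early termination, so that component otherwise depends on 9.13 repeats. The symptom component needs adverse event data. The cost is a small amount of table programming and some near-empty cells. Trial conduct, sample size and efficacy analyses are unchanged.

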3.8.4 Physical Examination

The number and percentage of patients with abnormal physical examination findings will be presented for the Safety Population.

3.8.5 Vital Signs, Weight, Height, BMI

Vital signs parameters will be summarized using descriptive statistics for the Safety Population. The change from baseline will also be presented.

3.8.6 Other Safety Parameters

Other safety data will be listed.

3.9 Pharmacokinetic Analysis

Blood samples for PK assessments will be obtained pre-dose from patients at the Baseline Visit (Day 1), and at Weeks 2, 8, and 12, and the Early Termination Visit. Blood samples for PK assessments will also be obtained 4 hours post-dose at Week 2 to inform the MGL-3196 dosing starting at Week 4. Statin PK will be assessed at baseline and Week 2 and may be assessed at later visits as well.

PK concentrations will be summarized descriptively.

Concentration of statins and PK concentration of MGL-3196 will be assessed to determine any drug interactions or relationship to safety.

3.10 Interim Analysis

There is no planned interim analysis for this study.

4. SAMPLE SIZE DETERMINATION

Up to 105 patients in total will be randomized to 1 of 2 treatments (70 patients to MGL-3196, 35 patients to placebo). It is estimated that the treatment difference of percent change in LDL-C from baseline to Week 12 between any dose of MGL-3196 group and the placebo group is about -20%. With a common standard deviation for the change in LDL-C at 20%, 27

patients per group to complete the Week 12 visit will provide 90% power with a two-sample t-test. The significance level is set as 0.025 for the consideration of multiplicity in comparisons of 2 daily dosing regimens of MGL-3196 vs. placebo group. The enrollment size is designed to allow for dropouts before the 12-week visit, and as such, patients who drop out of the study will not be replaced.

5. PROGRAMMING SPECIFICATIONS

Statistical analyses will be performed using SAS® (Cary, NC) version 9.3 or above. All available data will be presented in patient data listings, which will be sorted by site number, unique patient identifier and where appropriate, visit number and visit/assessment date.

The programming specifications, including mock-up validity listings, analysis tables, figures, and data listings, as well as the derived database specification, will be prepared in stand-alone documents.
